## 4 Study Design

This is a Phase 1/2, open-label study in subjects undergoing head and neck surgery. The study will include up to 6 Dose Escalation/De-Escalation cohorts, followed by 2 pre-planned additional Dose Timing cohorts. Dose cohorts will start at 100 mg and follow the escalation/de-escalation described in the protocol.

Indication	Parotid Neoplasm, Thyroid Neoplasms, Head and Neck Neoplasms, Head and Neck Surgery
Design	Open-label study: Dose Escalation/Dose De-Escalation and Dose Timing cohorts

QMS Document Name: Statistical Analysis Plan	Page 7 of 29
QMS No (include version ref): STF-015-GL.02	Document date: 09JUL2019
CONFIDENTIAL	

Phases	Phase 1/2
Primary Objective	To evaluate the safety of ALM-488 administered by intravenous (IV) infusion to subjects undergoing head and neck surgery.
Secondary Objectives	
 
• To characterize the pharmacokinetics (PK) of ALM-488 in subjects undergoing head and neck surgery.
 
• To determine the recommended dose of ALM-488 needed to generate an adequate fluorescence signal in nerves.
 
• To evaluate the effect of timing of administration of ALM-488 relative to surgery (e.g., up to 5 hours before surgery) on adequacy of fluorescence nerve labeling.
 

Exploratory Efficacy Objectives	
 
• To evaluate the ability of imaging techniques (i.e. camera systems) to distinguish nerve tissue from non-nerve tissue.
 
• To evaluate the intensity of signal of fluorescence relative to nerve diameter.
 
• To evaluate the intensity of signal of fluorescence when there is overlying tissue.
 
• To assess the depth of fluorescence penetration when there is overlying non-nerve tissue.
 
• To evaluate surgeon confidence and operating time with a surgeon rating scale.
 

Treatment	ALM-488 Sterile Solution is an intravenously administered, synthetic, peptide dye conjugate indicated for the real-time intraoperative fluorescence detection and localization of nerve tissue.
Number of subjects	9-36 subjects in the Dose Escalation/De-Escalation cohorts 12 subjects in the Dose Timing Cohorts Total 21-48 subjects
Interim analysis	No formal interim analysis is planned for this study
Planned enrolment	Three sites in the United States.

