#### **4.1 Sample Size Estimation**

The primary objective of this study is to evaluate the safety of ALM-488 administered by intravenous (IV) infusion to subjects undergoing head and neck surgery.

At each dose level, a cohort of 3 subjects will be enrolled for safety and tolerability evaluation. If there are no subjects with a DLT at a given dose level, new subjects will be enrolled at the next dose escalation level. If there are  $\geq 1$  subjects having any DLT, the enrollment to that specific dose and dose escalation will stop. New subjects will be enrolled at the next dose de-escalation level. There will be a minimum of 3 cohorts. Given that there will be 3-6 subjects for each dose level, 9-36 subjects will be needed for the dose escalation/de-escalation cohorts.

It is anticipated that the proposed dose range (100-1000mg) is expected to yield optimal imaging performance, with an initial starting dose of 100mg that has been selected based on supportive nonclinical testing. If the 100 mg dose is found to provide adequate fluorescence imaging of nerves, a dose de-escalation schedule will be followed to ensure that the lowest effective dose is determined. If imaging at starting first de-escalated dose (75 mg) becomes less adequate compared to 100mg as determined by the SRC, then imaging at dose escalation schedule will resume - beginning at 200mg. The Optimal Dose will be determined by the SRC as the lowest possible dose and toxicity profile that achieves adequate imaging performance of nerves using WLR combined with FL.

The Dose Timing Cohort will use the Optimal Dose as defined by the SRC following completion of the Dose Escalation/De-Escalation cohorts. Subjects in the Dose Timing phase will be administered ALM-488 at two planned operative times before surgery to assess the impact of timing of administration on fluorescence image quality. This phase will consist of 2 cohorts, 6 subjects/cohort: (1) dose administration 3-5 hours in advance of surgery, (2) dose administration 1-3 hours in advance of surgery. A total of 12 subjects will be needed for the Dose Timing phase.

In summary, 9-36 subjects may be enrolled into the dose escalation/dose de-escalation cohorts and 12 subjects may be enrolled into the dose timing cohort. A total of 21-48 subjects may be enrolled into this study.

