The optimal cut-off points of SBR and the ability to detect the nerve will be studied using ROC (Receiver Operating Characteristics) curves analyses through logistic regression. In the logistic regression the outcome variable will be the categorized surgeon rating scale 1 : I do not see the nerve versus 4 to 5 : the nerve is visible. The Youden J index given by  $J = \text{Sensitivity} - (1 - \text{Specificity})$  will be used to select the optimal predicted probability cut-off. It is the maximum vertical distance between ROC curve and diagonal line. This will allow to maximize the difference between True Positive and False Positive. All possible SBR values and the corresponding sensitivity and specificity will be obtained using proc logistic in SAS [1]. The optimal cut-off will be determined overall and by device and individual Cohorts (i.e., Cohorts: A, A1, A2, A3, A4, A5, A6, B, B1, B2).

Image intensity ratios will be plotted against nerve diameter, with ratios on the y-axis and diameters on the x-axis. Plots will be displayed overall and by device and individual Cohorts (i.e., Cohorts: A, A1, A2, A3, A4, A5, A6, B, B1, B2).

QMS Document Name: Statistical Analysis Plan	Page 19 of 29
QMS No (include version ref): STF-015-GL.02	Document date: 09JUL2019
CONFIDENTIAL	

Image intensity ratios will be summarized separately for images with and without overlying tissue, overall and by device and individual Cohorts (i.e., Cohorts: A, A1, A2, A3, A4, A5, A6, B, B1, B2).

In the subset of images with overlying non-nerve tissue, depth will be measured via the amount of overlying tissue that there can be to still maintain the ratio of nerve to non-nerves. Depth will be summarized overall and by device and individual Cohorts (i.e., Cohorts: A, A1, A2, A3, A4, A5, A6, B, B1, B2).

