#### EFFICACY

- Table 14.2.2.1 SBR comparison between FL and WLR, Zeiss camera Cohort A Analysis Set: FAS
- Table 14.2.2.2 SBR comparison between FL and WLR, Cohort B Analysis Set: FAS

- Table 14.2.3.1 SBR comparison between FL and WLR – Zeiss Image Analysis, Cohort A Analysis Set: FAS
- Table 14.2.3.2 SBR comparison between FL and WLR – Image Analysis, Cohort B Analysis Set: FAS

- Table 14.2.4.1 SBR comparison between B1and B2 – FL Analysis Set: FAS

- Table 14.2.4.2 SBR comparison between B1 and. B2– WLR Analysis Set: FAS

- Table 14.2.5.1 Surgeon Rating Scale, Cohort A Analysis Set: FAS

- Table 14.2.5.1 Surgeon Rating Scale, Cohort B Analysis Set: FAS

- Table 14.2.6.1 Correlation Between Surgeon Rating Scale and SBR for Zeiss device, Cohort A - Analysis Set: FAS

- Table 14.2.6.2 Correlation Between Surgeon Rating Scale and SBR, Cohort B Analysis Set: FAS

- Table 14.2.7.1 SBR and Surgeon Rating Scale for Zeiss device Cohort A, FL Analysis Set: FAS

- Table 14.2.7.2 SBR and Surgeon Rating Scale Cohort B, FL Analysis Set: FAS

- Table 14.2.8 Optimal cut-off point of SBR Cohort A and B, FL- Analysis Set: FAS

- Table 14.2.9.1 Surgeon nerve dissecting time saved, Cohort A Analysis Set: FAS

- Table 14.2.9.1 Surgeon nerve dissecting time saved, Cohort B Analysis Set: FAS

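### The SBR cut-off is chosen and scored on the same images, so in single cohorts of 3-6 patients its sensitivity and specificity in Table 14.2.8 will be materially too high

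*SAP*

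**What the plan says.** SAP Section 13.1 fits a logistic regression with the surgeon rating as outcome (1 against 4-5; ratings 2 and 3 fall in neither class). Youden's J "will be used to select the optimal predicted probability cut-off", and PROC LOGISTIC supplies the sensitivity and specificity at each SBR value. The exercise is repeated at every level: "The optimal cut-off will be determined overall and by device and individual Cohorts", which the SAP lists as A, A1 to A6, B, B1 and B2. The output is "Table 14.2.8 Optimal cut-off point of SBR Cohort A and B, FL- Analysis Set: FAS" (Section 20.1).

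On cohort size, Section 4.1 says: "Given that there will be 3-6 subjects for each dose level, 9-36 subjects will be needed" for the dose cohorts. For the timing cohorts it says: "This phase will consist of 2 cohorts, 6 subjects/cohort". Ratings are made per image (Section 13.2). SBR analyses in Cohort A use Zeiss images only (Section 13). Section 7.3 makes the cut-off an exploratory endpoint.

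The available text names no hold-out sample, cross-validation or bootstrap for this analysis. It also sets no direction for the SBR-rating relation, no minimum number of rating-1 images and no handling of repeated images within a patient.

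**The concern.** A cut-off chosen to maximise J in a sample fits that sample's noise as well as its signal. Scoring it on the same images gives a J that is too high on average, and the fewer the images, the larger the excess. Several images from one patient carry less information than the same number from different patients. Section 13.1 averages images to one value per patient for its t-tests, but has no counterpart here.

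There is a second, smaller problem. The cut-off is taken on the fitted probability, so the sign of the fitted slope decides which side of the SBR scale is called visible. If SBR happens to be lower in the well-rated images of a small cohort, the rule becomes low SBR means nerve visible.

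Table 14.2.8 would put up to eight single-cohort cut-offs (A1-A6, B1, B2) beside the pooled ones. Chance differences between them could be read as effects of dose, timing or camera, and the sensitivities and specificities would look better than new images would show.

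**Working it through.** **Enrolment.** Dose cohorts: "There will be a minimum of 3 cohorts" and "The study will include up to 6 Dose Escalation/De-Escalation cohorts", each with 3-6 patients. Minimum 3 × 3 = 9; maximum 6 × 6 = 36. Timing cohorts: 2 × 6 = 12. Totals: 9 + 12 = 21 and 36 + 12 = 48, which agrees with "A total of 21-48 subjects may be enrolled into this study". The documents give no image count and no precision target for the ROC analysis, so its size has to be simulated under stated assumptions.

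**Quantities.** J = sensitivity + specificity − 1. *Apparent* J is the maximum over cut-offs in the cohort's own images. *Actual* J is that same cut-off scored on new images. In a one-predictor logistic model the slope has the sign of (mean SBR in images rated 4-5) − (mean SBR in images rated 1), and this fixes the direction.

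**Main simulation.** Assumed: two thirds of images rated 4-5; SBR and latent rating each with patient and image components (within-patient correlation 0.5); latent correlation 0, 0.4 or 0.6, giving best attainable J of 0, 0.27 or 0.42. The chosen cut-off was scored in a population of 200,000 images.

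| Patients × images | Images | Apparent J, no relation (actual 0) | Apparent J, best 0.42 | Actual J, best 0.42 | Excess |
|---|---|---|---|---|---|
| 3 × 4 | 12 | 0.54 | 0.68 | 0.31 | 0.37 |
| 3 × 8 | 24 | 0.43 | - | - | - |
| 6 × 8 | 48 | 0.30 | 0.54 | 0.37 | 0.17 |
| 30 × 8 (pooled) | 240 | 0.13 | 0.46 | 0.40 | 0.06 |

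Reversed direction: about 7% of 3 × 4 cohorts when the best attainable J is 0.42 and 18% when it is 0.27; under 1% at 6 × 8 with best J 0.42.

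**Different assumptions.** With normal SBR, within-patient correlation 0 or 0.3, 50-80% of images rated 4-5, and single cohorts of 9-36 images:

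- True AUC 0.5: apparent J 0.27-0.63, actual 0. For example, 18 images with 80% rated 4-5 show sensitivity 0.67 and specificity 0.81 (J = 0.48), against true values of 0.58 and 0.42 (J = 0).
- AUC 0.75: 0.49-0.72 against 0.22-0.33.
- AUC 0.9: 0.73-0.87 against 0.51-0.60; reversal at most about 2%.
- Pooled sets of 216-288 images: excess about 0.10-0.15, 0.04-0.08 and 0.03-0.06 at AUC 0.5, 0.75 and 0.9.
- Some cohorts allow no cut-off because all images fall in one class: up to 19% with 9 images at 80% rated 4-5.

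**Does validation repair it?** One pooled cut-off, direction fixed in advance, 80% rated 4-5, within-patient correlation 0.3:

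| Pooled set | True AUC | Apparent J | Leave-one-patient-out J | Actual J |
|---|---|---|---|---|
| 21 × 3 | 0.5 | 0.18 | 0.00 | 0.00 |
| 21 × 3 | 0.75 | 0.49 | 0.33 | 0.33 |
| 21 × 3 | 0.9 | 0.72 | 0.59 | 0.60 |
| 48 × 6 | 0.5 | 0.09 | 0.01 | 0.00 |
| 48 × 6 | 0.75 | 0.41 | 0.35 | 0.35 |
| 48 × 6 | 0.9 | 0.67 | 0.62 | 0.62 |

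Leave-one-patient-out scoring removes essentially all of the excess, and a preset direction rules out reversal.

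**The case against.** The best case for the plan is that this is one exploratory table. Section 8.3 says that results by cohort and camera are descriptive, and nothing says the in-sample values will be presented as validated performance. Pooled cut-offs are already planned, and there the excess is modest. Images per patient are unknown: with 6 patients × 20 images, AUC 0.9 and 80% rated 4-5, apparent J is 0.71 against 0.60, an excess of 0.11. A reversed cohort would be noticed, because Section 13.2 correlates SBR with the rating by cohort. Table specifications are held in a separate document (Section 2.1), which is not available here.

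Most of this stands as a limit on the size and consequence. It does not remove the defect. The correlation would expose a reversal but not the overstatement, and an exploratory table still misleads if it shows discrimination that is not there.

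A reader might go further in three ways that do not hold:

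- *That the in-sample AUC can never fall below 0.5.* The slope follows class means while AUC follows ranks. With visible SBR 1, 1.1, 1.2, 6 and not-visible 1.8, 1.9, 2.0, the slope is +0.17 and the AUC is 3/12 = 0.25. About 5% of no-relation cohorts fall below 0.5.
- *That reversal is a general threat.* It matters only with few images and weak discrimination.
- *That the dose could be chosen wrongly on this cut-off.* Sections 4, 4.1 and 12 leave the Optimal Dose to the Safety Review Committee's view of toxicity and adequate fluorescence; none of them refers to the cut-off.

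**Conclusion.** The concern holds for the single-cohort cut-offs and should be acted on. Choosing and scoring the cut-off on the same images overstated J in every single-cohort setting tested. Under the main assumptions the excess is 0.30-0.54 when SBR is uninformative and 0.17-0.37 when the best attainable J is 0.42. In pooled sets it is modest (0.06 and 0.13 at 30 × 8).

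The direction of the bias follows from the method. Its exact size depends on image counts, the rating split and the within-patient correlation, none of which the documents give. The consequence is misleading values in Table 14.2.8, and chance differences between cohorts that could pass for dose, timing or camera effects. The primary safety conclusion is not affected.

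**What to change.** In Section 13.1 and Table 14.2.8:

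1. Drop the cut-offs for A1-A6, B1 and B2, and keep per-cohort SBR descriptive.
2. Derive cut-offs only in pooled sets (overall and by device), with the direction fixed in advance: higher FL SBR means nerve visible.
3. Report apparent and leave-one-patient-out sensitivity and specificity side by side, with 95% confidence intervals from a bootstrap that resamples patients.
4. Fix in advance a minimum number of rating-1 images, and report no cut-off for a pooled set that falls short. This may affect OnLume, whose SBR data come only from the 12 Cohort B patients.
5. Applying the Cohort A Zeiss cut-off to Cohort B can be a supplement only if Cohort B has enough rating-1 images. It should not be the main validation: Cohort B is treated at a dose already judged adequate, so such images may be few or absent. With 4 of 5 classified correctly, the exact 95% interval for specificity is 28-99%, before clustering.

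Cost: SAP wording and a short program, with no new data. Per-cohort cut-offs disappear and the validated sensitivity and specificity will be lower than the apparent ones.

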### **13.2 Surgical Imaging Worksheet/ Rating Scale**

Surgeon confidence will be captured via the surgeon rating scale (1=do not see nerve , 2=see nerve less well compared to WLR, 3=see nerve equally well compared to WLR, , 4=see nerve better compared to WLR, 5=see nerve much better compared to WLR ) for each image. Surgeon confidence will be summarized overall and by device, individual Cohorts (i.e., Cohorts: A, A1, A2, A3, A4, A5, A6, B, B1, B2) as well surgery type.

Image intensity ratios will also be correlated with the surgeon rating scale using Pearson correlation coefficients unless markedly non-normal data is observed including bimodal or other severe assumption violations; otherwise Spearman correlation coefficients will be used. Correlation coefficients will be presented overall and by device and by individual Cohorts (i.e., Cohorts: A, A1, A2, A3, A4, A5, A6, B, B1, B2).

A listing will be provided.

### **13.3 Clinical Benefit ALM-488 Questionnaire**

Clinical benefit for intraoperative nerve visualization questionnaire will be listed by individual Cohorts (i.e., Cohorts: A, A1, A2, A3, A4, A5, A6, B, B1, B2) for each patients and type of surgery.

### **13.4 Nerve Dissecting Time**

For each surgery, the following yes/no question will be asked: Outside of a clinical trial setting with all the required extra documentation, would this technology have saved you operative nerve-dissecting time compared to WLR alone (yes/no)?

Counts and percentages will be summarized overall and by device and individual Cohorts (i.e., Cohorts: A, A1, A2, A3, A4, A5, A6, B, B1, B2).

## **14 Safety**

All safety analyses will be completed on the SAF Analysis Set.

### **14.1 Adverse Events**

All information obtained on AEs will be displayed by treatment and patient. The number and percentage of subjects with AEs will be tabulated by System Organ Class (SOC) and Preferred Term (PT) with a breakdown by treatment. A patient with multiple AEs events within a SOC is only counted once towards the total of this SOC.

AEs will be coded using MedDRA version 23.1 or higher and presented by SOC and PT.

QMS Document Name: Statistical Analysis Plan	Page 20 of 29
QMS No (include version ref): STF-015-GL.02	Document date: 09JUL2019
CONFIDENTIAL	

The analysis will focus on the treatment-emergent AEs (TEAE), i.e., AEs which started or worsened on or after the study ALM-488 infusion and before the end of the study.

Number and frequencies of subjects with TEAEs as well as the number of events will be given by SOC and by PT within each SOC overall and by individual Cohorts (i.e., Cohorts: A, A1, A2, A3, A4, A5, A6, B, B1, B2) for the following:

- Any AE
- AE type
- At least one TEAE
- Serious TEAEs
- TEAE by CTCAE
- Infusion reactions IR overall and by CTCAE
- Related TEAEs
- Adverse Device Effects
- All TEAEs by maximum intensity

The counts and percentages of subjects with TEAEs as well as number of events will be presented by SOC and by PT and by decreasing frequency for:

- All TEAEs
- IR
- Serious TEAEs.
- Related TEAEs
- Serious Related.
- TEAEs leading to study discontinuation (if occurring in more than 5 subjects, otherwise a listing will be sufficient)
- Adverse Device Effects
- All TEAEs by intensity.
- All related TEAEs by intensity
- All TEAEs by outcome

Additionally, number and frequencies of subjects with TEAEs and number of events will be presented by PT and by decreasing frequency for

- All TEAEs
- Serious TEAEs
- Related TEAEs.

QMS Document Name: Statistical Analysis Plan	Page 21 of 29
QMS No (include version ref): STF-015-GL.02	Document date: 09JUL2019
CONFIDENTIAL	

Finally, a summary of Serious TEAEs and deaths by individual Cohorts and for all patients

Listings will be created for

- All AEs
- Serious AEs (SAEs)
- AEs leading to discontinuation of study medication
- AEs leading to discontinuation from study
- AEs leading to death

and will also include subjects screened but not infused with ALM-488.

If severity is missing, the event will not be included in the frequency tables presenting events by intensity. If relationship to study drug is missing, the event will be assessed as unrelated if it started before start of study medication; in all other cases it will be assumed to be related.

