## **7 Endpoints**

### **7.1 Safety Endpoints**

The endpoints to assess the safety of ALM-488 include:

- Adverse Events (TEAEs)
- Vital signs
- Clinical laboratory evaluations
- ECGs
- Physical examinations

Summaries of AEs will be based on Treatment Emergent Adverse Events (TEAEs) and will be summarized separately for each device and each of the Cohorts A1-A6, B1 and B2, as well as overall for Cohort A and Cohort B.

Vital signs, labs, ECGs, and physical exams will be summarized separately for each of the Cohorts A1-A6, B1 and B2, as well as overall for Cohort A and Cohort B.

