### **8.7 Study Day, Visit Window, and COVID-19**

For each patient, the day of surgery will be considered Study Day 1. Each assessment will be assigned a study day. The calculation for study day is dependent on whether the actual date of assessment is before or after the date of study Day 1 and is calculated as follows:

Before study Day 1:

study day = (date of assessment – Date of first dose of study medication Day 1).

On or after study Day 1:

study day = (date of assessment – Date of first dose of study medication Day 1) +1.

Days within the screening period will be numbered with negative numbers until day -1 defined as the day before AML-488 treatment (Day 1).

If the full date of the assessment is not known or not imputable based on the guidelines in Section 7.3, then no study day will be assigned. Study Day, and any corresponding durations will appear partial or missing in the listings.

For each patient, the end of the study is defined as the date of their last contact in this study.

Data will be analyzed based on the categorized visit captured in the database. No dates will be used to reassign visits or define visit windows. Although Day 15 or Early Termination is defined with +/-8 days, extensions to the visit window may be allowed due to impacts related COVID-19. Although Day 28/End of Study is defined with +/- 5 days, extensions to the visit window may be allowed due to impacts related COVID-19.

Any impacts due to COVID-19 will be noted in the study documentation.

The visits captured in the database include:

- Screening (Day -28 to Day -1)
- Baseline (Day 1) (pre- and post-operative)
- Day 15 or Early Termination

QMS Document Name: Statistical Analysis Plan	Page 15 of 29
QMS No (include version ref): STF-015-GL.02	Document date: 09JUL2019
CONFIDENTIAL	

- Day 28/End of Study

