### 9.2 *Disposition and withdrawals*

The number and relative frequency will be presented for

- Subjects completing the study
- Subjects who prematurely discontinued the study
- Reasons for study discontinuation (Adverse Event, death, lost to follow-up, physician decision, pregnancy, progressive disease, site or study terminated by sponsor, technical problems, withdrawal by subject, adverse device effect or other)
- Subjects completing surgery
- Subjects completing treatment

Completing the study is defined as having completed the infusion, surgery, and end of study telephone call.

A list of subjects' trial end date, time to trial discontinuation and reason for trial discontinuation will be created.

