## 18 Statistical Analyses for Clinical Trial Registries

The following additional analyses will be performed for the purpose of fulfilling the Clinical Trial Registry (CTR) requirements:

Both Serious Adverse Events and Non-Serious Adverse Events will be summarized by MedDRA preferred term.

- An adverse event is considered 'Serious' whether or not it is a TEAE
- An adverse event is considered in the 'Non-Serious' category if it is both a TEAE and is not serious

For each Serious AE and Non-Serious AE, for each term and treatment group, the following are provided:

- the number of subjects at risk of an event;
- the number of subjects who experienced each event term;
- the number of events experienced.

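### The TEAE window closes before the date of last contact, so an adverse event that starts or worsens on that date is left out of the TEAE tables

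*SAP*

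**What the plan says.** Section 14.1 of the SAP (Adverse Events) centres the safety analysis on TEAEs, defined as "AEs which started or worsened on or after the study ALM-488 infusion and before the end of the study". Section 8.7 (Study Day, Visit Window, and COVID-19) supplies the closing date: "For each patient, the end of the study is defined as the date of their last contact in this study". For a subject who completes the study, the final planned contact is a telephone call, because Section 9.2 states: "Completing the study is defined as having completed the infusion, surgery, and end of study telephone call".

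Section 7.1 bases the adverse event summaries on TEAEs. Most adverse event tables in Section 20.1 follow suit: all, serious, related, leading to discontinuation, by intensity and by outcome.

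Some outputs are not limited to TEAEs:

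- Section 14.1 names any AE as a row, and Table 14.3.1.1 is an overview of adverse events as well as TEAEs.
- Section 14.1 plans listings of all AEs, serious AEs, AEs leading to discontinuation and AEs leading to death.
- It also plans a table in which deaths are named beside serious TEAEs: "Finally, a summary of Serious TEAEs and deaths by individual Cohorts and for all patients".
- Section 18 counts serious events for the registry whatever their TEAE status. For the rest it says: "An adverse event is considered in the 'Non-Serious' category if it is both a TEAE and is not serious".

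**The concern.** The lower bound of the window is inclusive and the upper bound is exclusive. The upper bound is also not a fixed day. It is each patient's own last contact, and an adverse event can determine when that is. A fatal event, or one that makes a subject withdraw the same day, can itself fix the last-contact date and so fall on the one day after infusion that the rule leaves out. Exclusion then depends on outcome, and it leans towards events that end participation.

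Safety is the primary objective, and the cohorts have 3 to 6 subjects, so a single event decides whether a row in a cohort column reads zero. The outputs would also disagree with each other. A serious event on the last-contact day would appear in the registry summary and in the serious AE listing but not in Table 14.3.1.4 (serious TEAEs). A non-serious one would appear in the listing of all AEs but in neither the registry summary nor the overall TEAE tables.

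**Working it through.** No figure in the plan depends on this definition, so there is none to reproduce. The check applies the rule to dated examples.

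**Inputs**

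- Window opens on the infusion and includes it (Section 14.1).
- Window closes before the end of study (Section 14.1), which is the date of last contact, given without a time of day (Section 8.7).
- Day 1: "For each patient, the day of surgery will be considered Study Day 1". The study-day formula in the same section counts from the first dose. The examples take infusion and surgery to fall on the same day.
- Subjects per dose level 3 to 6; Cohort A in total 9 to 36; each timing cohort 6, so 12 in Cohort B (Section 4.1).

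**Rules compared**

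- As written: TEAE if 1 ≤ onset day < last-contact day.
- Inclusive: TEAE if 1 ≤ onset day ≤ last-contact day.

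Onset here means start or worsening. The days are illustrative and lie within the SAP's visit schedule.

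| Example | Onset | Last contact | As written | Inclusive |
|---|---|---|---|---|
| Fatal event on the day of surgery | 1 | 1 | No | Yes |
| Day 1 event, subject followed to final call | 1 | 28 | Yes | Yes |
| Event on day of withdrawal, no later contact | 15 | 15 | No | Yes |
| Event leads to termination, seen at a later early-termination visit | 10 | 15 | Yes | Yes |
| Event starts on day of final call | 28 | 28 | No | Yes |
| Event started earlier, still present at final call | 20 | 28 | Yes | Yes |
| Event started the day before, still present at final call | 27 | 28 | Yes | Yes |

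Three of the seven change status, and in each the onset date equals the last-contact date. The other four are TEAEs under both rules.

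The date-imputation rule in Section 8.4 does not rescue these cases. For treatment-emergent status it sets an incomplete start date to the date of first dose unless there is clear evidence otherwise. If last contact is also on that date, the imputed onset still fails the test 1 < 1.

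**Size of one lost event**, in a row where it is the only event:

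- 3-subject cohort: 1/3 = 33.3%, reported as 0/3.
- 6-subject cohort: 1/6 = 16.7%, reported as 0/6.
- Cohort B overall: 1/12 = 8.3%, reported as 0/12.
- Cohort A overall: from 1/9 = 11.1% down to 1/36 = 2.8%, depending on enrolment, reported as zero.

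The documents give no basis for estimating how often onset will fall on the last-contact day, so these are sizes per event and not expected losses.

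**The case against.** The strongest reply is that this is loose wording and not an intended exclusion. Section 8.4 leans the other way, since it treats events with uncertain dates as treatment-emergent. A programmer might well code the bound inclusively, or compare clock times so that an event a few hours before the final call would count. The conservative intent is plausible. However, Section 8.7 defines the end of study as a date only, no section makes the bound inclusive, and Section 2.1 requires departures from the SAP to be documented and justified in the study report. The text should say what is meant.

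The reply is right about how far the problem reaches. Several stronger readings are tempting, and the documents do not support them:

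- *Any event present at the final call is lost.* The rule turns on start or worsening, so an event that began earlier and is merely continuing remains a TEAE.
- *The events vanish from the report.* They stay in the AE, serious AE, discontinuation and death listings, in the any-AE row and, if serious, in the registry summary.
- *A Day 1 death goes uncounted.* Section 14.1 names deaths separately from serious TEAEs, so a death can still be counted there. The title of Table 14.3.1.15 leaves open whether its deaths are limited to treatment-emergent ones, which is a reason to state it.
- *Every participation-ending event is affected.* Any contact on a later date, such as the early-termination visit in Section 8.7, keeps the event in the window. The discontinuation table is also required only if more than 5 subjects are involved; otherwise a listing of AEs suffices.
- *Dose decisions are distorted.* The DLT Evaluable Set in Section 5 has its own evaluation period and does not use TEAE status.
- *The tolerance on the final visit is part of the fault.* The spread in follow-up comes from the visit window and is the same whether the TEAE bound is inclusive or exclusive.

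**Conclusion.** The definition is wrong as written, within a narrow scope. An adverse event that starts or worsens on the date of last contact is not a TEAE. It is therefore left out of the TEAE incidence tables (all, serious, related, by intensity, by outcome) and, if non-serious, out of the registry summary. One such event can change a cohort's rate from 1/3 to 0/3 or from 1/6 to 0/6.

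This rests on three assumptions: the SAP is applied literally, dates are compared by day, and last contact falls on the day of onset. The per-cohort figures also assume that no other event falls in the same table row. How often this will happen is unknown and may be seldom. The correction is worth making because the excluded date is one that a fatal or participation-ending event can itself set, because safety is the primary objective, and because the repair costs almost nothing.

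**What to change.** In SAP Section 14.1, change the upper bound of the TEAE definition to: on or before the date of last contact. Add one sentence stating that the deaths part of Table 14.3.1.15 counts all deaths after infusion, whatever their TEAE status.

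The cost is two short edits to the SAP, a change from < to ≤ in the TEAE flag, and a check that the deaths count is not filtered on that flag. No new data are needed. The one downside is that reported TEAE counts may rise slightly. A fixed minimum follow-up day is not needed to repair this fault, and the available protocol text does not give an adverse event collection period against which to set one.
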